### 12.2 Analysis of Primary Endpoint

The primary analysis will use the modified Intention-to-Treat (mITT) population consisting of subjects who are enrolled and received any dose of study medication. The mITT population will be included in summary tables of subject demographics and disease characteristics, and in analysis of efficacy. Subjects who did not progress to surgery (for any reason) or are lost to follow-up will be censored at the day of their last objective tumor assessment and will be unevaluable for the primary endpoint. Subjects failing to proceed to surgery will be replaced, but all will support the secondary endpoints including feasibility, safety and correlative biologic analyses.

Post-operative complications will be measured at the EOT visit 4-6 weeks after surgery. Complications occurring within 30 days after surgery and contributing to the primary endpoint are defined as hospital re-admission, death, second surgery or interventional procedure or major complications extending hospital stay. The proportion and its exact 90% confidence interval of 30-day post-operative complication rate will be calculated. Statistical analyses will be conducted using SAS v9.4 (SAS institute, Cary, NC).

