	
B. Locally advanced unresectable disease (see the criteria for resectability from inclusion criteria) or evidence of metastatic disease.
 
C. Any other invasive malignancy within the past three years.
 
D. Presence of any known contraindications to or hypersensitivities to the investigational products.
 
E. Use of strong CYP3A4 inhibitors or inducers, which cannot be discontinued prior to study entry.
 
F. A non-surgical candidate.
 
G. Subject is unable to understand, provide consent or comply with study requirements, treatments or instructions in the opinion of the treating physician.
 
H. Uncontrolled diarrhea, active infection, known interstitial lung disease or other medical condition that precludes safe administration of this combination therapy consistent with manufacturer recommendations.
 
I. Unwilling/unable to comply with birth control requirements while on study.
 
J. Females or males of childbearing potential who are unwilling or unable to use an acceptable method to avoid pregnancy for the entire study period and for at least 7 months for females and 4 months for males after the last dose of study drug.
 
K. Females who are pregnant or breastfeeding.
 
L. History of any other disease, metabolic dysfunction, physical examination finding, or clinical laboratory finding giving reasonable suspicion of a disease or condition that contraindicates the use of protocol therapy or that might affect the interpretation of the results of the study or that puts the subject at high risk for treatment complications, in the opinion of the treating physician.
 
M. Prisoners or subjects who are involuntarily incarcerated.
 
N. Subjects who are compulsorily detained for treatment of either a psychiatric or physical illness.
 
O. Subjects demonstrating an inability to comply with the study and/or follow-up procedures.
 
P. Known dihydropyrimidine (DPD) deficiency

Efficacy Assessments:	4 to 8 weeks after completion of neoadjuvant chemotherapy subjects will undergo surgical resection. The primary endpoint is the complication rate for evaluable patients who complete surgery, and

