	
this will be compared to expected complication rate. Pre-operative imaging will be compared to the baseline studies to assess radiographic response and continued surgical resectability potential. RECIST Radiographic criteria and clinical evaluations will be used to determine radiographic response and resectability. Surgical resection rates will be calculated and pathologic downstaging will be determined. Biochemical response rates will be calculated by serial CA19-9 levels and characterized as those with normalization of CA19-9 during therapy, reduction without normalization or no reduction with assessment of the temporal nature of these changes and correlation to surgical resection rates. Treatment completion rate will be calculated for all patients and is defined as the completion of all intended treatment cycles. Statistical analyses will be conducted by the study biostatistician using SAS v9.1 (SAS institute, Cary, NC)

Statistical Considerations:	
For this prospective phase II pilot study, the sample size justification is based on the primary endpoint, the complication rate for evaluable patients who complete surgery. A sample size of 25 patients achieves ~80% to detect a reduction of 20% in the 30-day post-operative complication rate (from 30% to 10%), using a one-sided exact test with a significance level of 0.05. Assuming 10% drop-out rate, we will accrue a total of 28 patients for this study. The study expects a 20-month accrual period with an additional follow-up of 7 months after the last patient is enrolled. Subjects failing to proceed to surgery will be replaced, but all will support the secondary analyses. The sample size calculation is conducted by PASS 16.

Estimated Enrollment Period:	20 months
Estimated Study Duration:	27 months

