## 8. TREATMENT DISCONTINUATION

### 8.1 Removal of Subjects From Study

Subjects who discontinue participation in the clinical study on their own or subjects who are withdrawn by the investigator, for reasons other than completion of treatment, disease progression or toxicity, will be defined as premature withdrawals. Subjects who are not initiated on study drug, but sign informed consent and undergo at least some of the screening procedures will be considered screening failures. A record of these patients will be maintained by the study site. Subjects who are treated with at least one full course of NALIRIFOX will contribute to the intention-to-treat analyses. Any subjects that do not complete surgery will be replaced, but all patients will contribute to the intention-to-treat design of the study and relevant endpoints.

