### 12.1 Sample Size Determination

For this prospective phase II pilot study, the sample size justification is based on the primary endpoint, the complication rate for evaluable patients who complete surgery. A sample size of 25 patients achieves ~80% to detect a reduction of 20% in the 30-day post-operative complication rate (from 30% to 10%), using a one-sided exact test with a significance level of 0.05. Assuming 10% drop-out rate, we will accrue a total of 28 patients for this study. The study expects a 20-month accrual period with an additional follow-up of 7 months after the last patient is enrolled. The sample size calculation is conducted by PASS 16.

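### The primary denominator is labelled any-dose mITT but is really operated subjects, and two unreconciled surgery triggers leave room for an intra-operative death or a complicated aborted resection to be replaced instead of counted

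*Combined protocol and SAP*

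**What the plan says.** Section 12.2 names the population: "The primary analysis will use the modified Intention-to-Treat (mITT) population consisting of subjects who are enrolled and received any dose of study medication". It then says that subjects who did not progress to surgery for any reason, or who are lost to follow-up, "will be censored at the day of their last objective tumor assessment and will be unevaluable for the primary endpoint". The 30-day events that count are "defined as hospital re-admission, death, second surgery or interventional procedure or major complications extending hospital stay". The planned output is a proportion with an exact 90% confidence interval.

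The documents describe in two ways which subjects are in and which are replaced:

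- **Completing surgery.** Section 12.1 bases the sample size on "the complication rate for evaluable patients who complete surgery". The synopsis (Efficacy Assessments) says "The primary endpoint is the complication rate for evaluable patients who complete surgery". Section 8.1 says "Any subjects that do not complete surgery will be replaced", and 8.3 repeats that rule.
- **Reaching surgery.** Section 12.2 says "Subjects failing to proceed to surgery will be replaced". The synopsis (Statistical Considerations) says "Subjects failing to proceed to surgery will be replaced, but all will support the secondary analyses". Section 11.2 also ties the end of SAE collection to whether the subject proceeds with surgery.

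The current text does not define a completed surgery. It does not mention intra-operative death, or an operation that is begun and abandoned.

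**The concern.** Two things are wrong with the denominator.

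First, the label and the rule in 12.2 disagree. An any-dose population includes subjects who were never operated on, yet the same paragraph takes them out of the primary endpoint. Censoring at the last tumour assessment is a time-to-event device and has no meaning for a 30-day binomial proportion.

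Second, the two triggers differ for exactly the cases that a perioperative safety endpoint is meant to catch. A patient who dies on the table, or whose resection is abandoned with a complication, has reached surgery but has not completed it. Under 12.2 that patient is evaluable. Under the wording of 12.1 the patient is not among those described, and under 8.1 and 8.3 the patient is replaced. Death is a listed primary event. In an open-label single-arm trial, the choice between the two readings could be made after the outcome is known.

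**Working it through.** **Inputs.** Null rate 30%, target rate 10%, one-sided exact test at 0.05, 25 analysable subjects, 10% drop-out, 28 accrued (12.1). The synopsis (Accrual Goal) and 4.1 call the 28 evaluable, so both sizes are shown. The interval is exact 90% (12.2).

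**Formulas.**
- One-sided p-value: P(X ≤ x | n, 0.30), the sum over k = 0 to x of C(n,k) × 0.30^k × 0.70^(n−k).
- Upper 90% limit: the rate p_U that solves P(X ≤ x | n, p_U) = 0.05. It falls below 30% exactly when the p-value is below 0.05.

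**The plan's own figures.**
- Accrual: 25/0.9 = 27.8, rounded up to 28. This reproduces.
- Power at n=25: P(X ≤ 3 | 0.30) = 0.0332 and P(X ≤ 4 | 0.30) = 0.0905, so the test succeeds at 3 or fewer events. Power is P(X ≤ 3 | 0.10) = 76.4%, not about 80%. An uncorrected normal approximation gives 79.4%. That gap is a separate matter, and nothing below depends on it.
- At n=28 the test succeeds at 4 or fewer events (0.0474).

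**Effect of one reclassified case at the boundary.**

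| Situation | Counted | Otherwise |
|---|---|---|
| Event replaced by a complication-free subject, n=25 | 4/25: p=0.0905, upper limit 33.0% | 3/25: p=0.0332, 28.2% |
| Same, n=28 | 5/28: p=0.1128, 33.9% | 4/28: p=0.0474, 29.8% |
| Replaced event added back to the 25 | 4/26: p=0.0733, 31.8% | 3/25: p=0.0332, 28.2% |

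Each row crosses the 30% line.

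**The opposite direction.** Start from 4/25 and add operations that were abandoned without a complication:
- one gives 4/26, p=0.0733
- two give 4/27, p=0.0591
- three give 4/28, p=0.0474, upper limit 29.8%, which is now a success

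**How often one case would decide.** At n=25 the full count must be exactly 4. The probability of that is 13.8%, 18.7% and 5.7% at assumed true rates of 10%, 20% and 30%. At n=28 the count must be 5, with probability 8.7%, 18.6% and 6.5%. These are chances of landing on the boundary, not chances that an intra-operative death or aborted resection occurs.

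**Why no net bias follows.** Let the true rate among all operated subjects be 30%. Let q be the share who are events in uncompleted operations and u the share who are uncomplicated uncompleted operations. If both are removed, the expected observed rate is (0.30 − q)/(1 − q − u).
- With u=0 and q=2%: 0.28/0.98 = 28.6%, and the chance of 3 or fewer events in 25 rises from 3.3% to 4.6%.
- With u=0 and q=4%: 0.26/0.96 = 27.1%, and that chance is 6.3%.
- With q=2% and u=4.67%: 0.28/0.9333 = 30.0%, so there is no shift at all.

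The values of q and u are assumptions. Section 1.1 gives only 30-day post-operative mortality (3.8–7.5%), which is neither of them.

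**The case against.** The strongest reply is that 12.2 is the analysis section and it governs. It makes unevaluable only those who did not reach surgery or were lost to follow-up, and it lists death as an event, so a death on the table counts. The synopsis mixes both wordings in one paragraph, which suggests loose synonyms. Section 8.1 adds that all patients still contribute to the intention-to-treat design and the relevant endpoints, so replacement need not mean exclusion.

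Much of this stands. A reader might infer that the plan instructs sites to drop intra-operative deaths. It does not: no passage orders that, and the current text uses completion of surgery as a description without defining evaluability by it. But 8.1 and 8.3 do say to replace, and 12.1 does describe the endpoint in completed operations. The clause about relevant endpoints does not say whether the primary one is among them. The conflict is open, and a site following 8.1 and 8.3 would be following the protocol.

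A second objection also stands in part. Counting every started operation can flatter the rate by adding uncomplicated aborted cases, as 4/28 shows. That is a reason to show a sensitivity analysis, not to leave the trigger open.

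A third is that the data may not all be there, and this stands. Section 11.2 stops collecting SAEs unrelated to a protocol procedure 30 days after the last dose, while surgery comes at 4–8 weeks. It also largely ends AE collection once another anti-cancer therapy starts. Section 8.2 places the end-of-treatment visit for a removed subject at removal or within 30 days. Thirty-day capture after an aborted operation is therefore not assured.

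**Conclusion.** The point holds as an unresolved contradiction, and it should be fixed. The mITT label is wrong for the primary endpoint, the censoring clause has no function there, and two triggers give different answers for an intra-operative death or a complicated aborted resection. One such case can reverse the conclusion when the full count is one above the critical value (4/25 against 3/25, or 5/28 against 4/28).

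Two stronger readings are tempting, and the documents do not support them. One is that the primary rate will be biased downwards: the frequency of such cases is not given, and uncomplicated aborted operations pull the other way, so neither size nor direction can be derived. The other is that the mITT label puts non-operated subjects in the denominator as complication-free: the unevaluable clause rules that out.

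The figures assume the exact test against 30% that the synopsis and 12.1 name. Section 12.2 itself promises only the estimate and its interval, whose upper limit leads to the same conclusions.

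**What to change.** - In 12.2, define the primary set as all subjects who received any study drug and in whom the planned operation was started. Define the start once, for example at first incision, with exploration before resection included.
- Use that trigger in the synopsis, 8.1, 8.3, 12.1 and 12.2. Delete the censoring clause. Keep any-dose mITT for the secondary endpoints.
- State that an intra-operative death is an event and that aborted operations are judged by the same 30-day criteria.
- Add one sensitivity analysis restricted to completed resections that still counts intra-operative deaths, because the documents do not say whether the 30% benchmark includes aborted operations.
- State that the primary-endpoint components are recorded to day 30 for every operated subject, including those whose resection is aborted, who are removed from study or who start new therapy. Reconcile this with 8.2 and 11.2.
- Report the number replaced, with reasons.

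Two additions are optional: a sensitivity row that counts operated subjects lost before day 30 as events, and a sentence on whether subjects replaced under 8.3 for new anti-cancer therapy count if they are still operated on.

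The cost is wording in five places, one sensitivity analysis, one count and a small clarification of data capture. The reported rate may move slightly in either direction.

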### 4.1 Number of Subjects

A total of 28 evaluable subjects are to be enrolled.

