### 12.3 Analysis of Secondary Endpoints

Secondary endpoints will also be analyzed in a similarly descriptive manner. Treatment completion rate is defined by the administration of all eight intended cycles of neoadjuvant chemotherapy. The surgical complete resection rate (R0) will be determined from review of the pathology reports and inclusive of pathologic nodal status and TNM staging (AJCC 8th Edition). Pre-operative imaging will be compared to the baseline studies to assess radiographic response, in those who have RECIST measurable disease at baseline. The radiographic objective response rate (RR) is equal to the proportion of patients achieving a best overall response of partial or complete response (CR + PR), according to RECIST from the start of the treatment until disease progression/recurrence. Clinical benefit rate is equal to the objective RR plus the proportion of patients attaining stable disease (CR + PR + SD). Patients with initially measurable disease who do not have a tumor response assessment for any reason will be considered non-responders and will be included in the denominator when calculating the response rate. Biochemical response rate is measured as

the difference between baseline and maximal nadir of serum CA19-9 level. Proportion and exact 95% CI based on binomial distribution will be estimated for each of the secondary endpoints described above. Subjects will further be characterized as those with normalization of CA19-9 during therapy, reduction without normalization or no reduction with assessment of the temporal nature of these changes and correlation to surgical resection rates. Secondary and exploratory endpoints may be characterized between those with resectable vs. borderline resectable disease at study entry, but without any planned formal analyses between these two subsets. Mean and 95% CI, assuming a normal distribution, median (range) will be estimated for quality of life (QOL) parameters using the FACT-G validated patient reported outcome instrument.

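### The lost-to-follow-up clause in Section 12.2 has no exception for operated subjects whose complication is already on record, so it can drop an observed primary event

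*Combined protocol and SAP*

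**What the plan says.** Section 12.2 names two groups for the primary endpoint: subjects who did not progress to surgery for any reason, and subjects lost to follow-up. Both "or are lost to follow-up will be censored at the day of their last objective tumor assessment and will be unevaluable for the primary endpoint". It sets no time limit on the loss and makes no exception for subjects who have been operated on.

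The same section states: "Post-operative complications will be measured at the EOT visit 4-6 weeks after surgery". It then defines the endpoint by when the event occurs, within 30 days of surgery: readmission, death, second surgery or interventional procedure, or a major complication that prolongs the stay. The planned output is the proportion with an exact 90% confidence interval. No success rule is written.

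Section 12.1 bases the sample size on "the complication rate for evaluable patients who complete surgery" and adds: "Assuming 10% drop-out rate, we will accrue a total of 28 patients for this study". Section 4.1 words the target differently: "A total of 28 evaluable subjects are to be enrolled".

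Sections 8.1 and 8.3 replace subjects who do not complete surgery. Neither mentions an operated subject who is lost afterwards.

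**The concern.** A complication can be on file before contact is lost. Section 11.2 collects serious adverse events up to the post-operative visit. Under Section 11.1.2, death, inpatient hospitalization and prolonged hospitalization are serious, and Section 11.4.1 requires reports within 24 hours to the project office and 5 days to the safety committee. A subject readmitted in the second week and then lost would have a documented primary event and yet be unevaluable under the wording of Section 12.2.

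If subjects with a complicated course are lost more often than others, for example because they are cared for elsewhere, the observed rate is biased downward, towards a favourable result. The trial is open-label and single-arm, its main purpose is perioperative safety, and with about 25 subjects one event can decide the result.

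**Working it through.** **1. Whom the clause reaches.** Every loss before surgery is already a failure to progress to surgery for any reason. What the words on loss to follow-up add is operated subjects. The censoring date does not help: the Schedule of Events (Appendix A) marks imaging only at screening and before surgery. For an operated subject the last tumor assessment therefore normally precedes the operation, and the whole 30-day window falls after it.

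**2. Inputs.** The null rate is 0.30, the target rate 0.10, and the test one-sided and exact at 0.05 (Synopsis: "from 30% to 10%), using a one-sided exact test with a significance level of 0.05"). There are 25 evaluable subjects (Section 12.1: "A sample size of 25 patients achieves ~80% to detect a reduction of 20% in the 30-day post-operative complication rate"). Accrual reproduces: 25/(1 − 0.10) = 27.8, rounded up to 28.

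**3. Formulas.** For x complications among n operated:
- p = Σ C(n,k) × 0.30^k × 0.70^(n−k), for k = 0 to x.
- The upper limit U of the exact 90% interval solves P(X ≤ x | n, U) = 0.05. U lies below 30% exactly when p < 0.05, so the test in 12.1 and the interval in 12.2 agree.

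**4. The plan's own figure.** At n = 25 the largest count with p ≤ 0.05 is 3. The exact level is 0.0332 and the power at 10% is P(X ≤ 3 | 25, 0.10) = 0.764. The stated ~80% matches the one-sided normal approximation (0.794), not the exact test named. That is a separate matter; what is used here is the cut-off of 3.

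**5. Dropping one complicated subject.** For 4/25, p = 0.03324 (0 to 3 events) + 0.05723 (exactly 4) = 0.09047.

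| All recorded events counted | p | Upper limit | One complicated subject dropped | p | Upper limit |
|---|---|---|---|---|---|
| 4/25 | 0.0905 | 33.0% | 3/24 | 0.0424 | 29.2% |
| 4/26 | 0.0733 | 31.8% | 3/25 | 0.0332 | 28.2% |
| 4/27 | 0.0591 | 30.8% | 3/26 | 0.0260 | 27.2% |
| 4/24 | 0.1111 | 34.2% | 3/23 | 0.0538 | 30.4% |
| 5/28 | 0.1128 | 33.9% | 4/27 | 0.0591 | 30.8% |

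The first three rows reverse; the last two do not. At n = 25, exactly 4 events has probability 0.057 if the true rate is 30% and 0.138 if it is 10%.

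**6. Effect on the type I error.** Take 25 operated subjects and a true rate of 30%. Suppose each complicated subject is lost with probability q and uncomplicated subjects never. With X the number of complications and D the number of those lost, sum P(X = x) × P(D = d | x) over all pairs for which (x − d)/(25 − d) passes the test:

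| q (assumed) | Type I error |
|---|---|
| 0 | 0.0332 |
| 5% | 0.0440 |
| 10% | 0.0540 |
| 20% | 0.0765 |

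The documents give no post-operative loss rate, so q is an assumption.

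**The case against.** The strongest reply is that the clause may be loose drafting. Loss to follow-up is not defined, and apart from 12.2 it appears only as a reason to stop treatment (Section 8.2). Censoring ordinarily concerns subjects without an event. The endpoint is defined by when the event occurs, not by attendance at a visit, and adverse events are followed to outcome (Section 11.3). On that view a careful analyst would count a recorded event anyway. This stands as a likely intention, but 12.2 does not say it, and its wording gives the opposite result.

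The reversal also needs a boundary count, and the rule does not always favour success: dropping one uncomplicated subject moves 4/28 (p = 0.0474) to 4/27 (p = 0.0591). The bias towards success depends on complicated subjects being lost more often, which is plausible but not documented. Both limits stand.

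Three stronger readings are tempting, and the documents do not support them:
- A reader might infer that missing the end-of-treatment visit is itself loss to follow-up. Nothing equates the two, and survival follow-up continues for 5 years (Section 6.5).
- A reader might infer that, because non-operated subjects are replaced, the 10% drop-out must be post-operative loss. No section says what it covers. The Synopsis states drop-out and replacement side by side, and Section 4.1 asks for 28 evaluable subjects, so the allowance may simply overlap with replacement.
- Section 12.3 says that measurable-disease subjects who "do not have a tumor response assessment for any reason will be considered non-responders" stay in the denominator, so a reader might infer that unknown status must count as failure here too. A rule for response rate does not oblige the same rule for the primary endpoint.

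**Conclusion.** The point holds in a limited form. As worded, Section 12.2 can remove an observed primary event from numerator and denominator, and no other section prevents it. In the boundary case one such removal takes p from 0.0905 to 0.0424 and the upper limit from 33.0% to 29.2%. Under the assumed selective losses of 5%, 10% and 20%, the type I error stays below 0.05, slightly exceeds it, and clearly exceeds it.

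This rests on a literal reading of the clause, on success inferred from the Section 12.1 test, and, for the type I figures, on 25 operated subjects with only complicated ones lost. It does not show that the rule was meant to delete events or that such losses are common.

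**What to change.** In Section 12.2:
- Count any qualifying event recorded within 30 days of surgery as a complication, whether or not the end-of-treatment visit takes place or the subject is later lost.
- Allow day-30 status to be obtained from hospital records or by telephone.
- Among operated subjects, treat as unevaluable only those with no recorded event and unknown day-30 status. Prespecify a sensitivity analysis that counts them as complications.
- Remove the tumor-assessment censoring wording, which has no role for a binary 30-day endpoint.

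Counting every unknown as a complication in the primary analysis is not recommended. With an assumed 28 operated subjects, 10% unknown at random and a true rate of 10%, power would be 36%, against 74% for complete cases.

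The cost is a few sentences and some effort to obtain day-30 status. The reported rate may be slightly less favourable.
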